6.1 Adverse Events

Adverse events will be recorded in the eCRF and will be coded according to the MedDRA dictionary Version 23.0. All AEs including SAEs will be collected up to 30 days after the last administration of IMP (or as of March 2nd., 2020, up to 30 days after the EOT) and followed until resolution.

A treatment-emergent adverse event (TEAE) is defined as an adverse event that started or worsened after the start of the administration of IMP. Treatment-emergent AEs will include AEs that occur after the first dose of IMP (i.e. day 1, Cycle 1) and end at the EOT visit (i.e. 14 days after the last dose of IMP). AEs will also be considered treatment-emergent if they are ongoing at first IMP infusion or start ≤ 30 days after the last dose of IMP. Adverse events with unknown start date/time will be assumed to be treatment-emergent unless the end date/time is known to be before administration of the first dose of IMP. Non-treatment emergent AEs will include any AEs that occur between informed consent and the first dose of IMP.

Allocation of AEs to study periods

All AEs and SAEs will be allocated to a study period depending on the onset date in relation to the date of administration of IMP:

Period 1: Time of informed consent until time before first dose of IMP (non-TEAE)

Period 2: Time of first dose of IMP until time of last dose of IMP + 30 days (TEAE)

Period 3: Time of last dose of IMP + 31 days and onwards (non-TEAE)

In case of complete or partial missing start or end date of an AE see details in Section 3.3.

Causality to the Investigational Medical Product (IMP)

- Not related
- Unlikely related
- Possibly related
- Probably related
- Definitely related

An AE/SAE is defined as related to IMP if the event is classified as Possibly, Probably or Definitely related.

Intensity of Adverse Events

- Mild
- Moderate
- Severe
- Life-threatening
- Death related to AE

No summaries will be done of AE/SAE by intensity but will be included in the listings.

Data presentations

If a patient experienced more than one TEAE the patient will be counted once for each SOC and once for each PT. System organ class and preferred terms will be ordered alphabetically first by SOC and then all PTs alphabetically within a SOC. Non-TEAEs will not be presented in summary tables, only in listings.

Tables: treatment-emergent AEs

- Number and percentage of patients experiencing TEAEs by SOC and PT for each treatment group and total
- Number and percentage of patients experiencing TEAEs leading to withdrawal of IMP by SOC and PT for each treatment group and total
- Number and percentage of patients experiencing TEAEs related to IMP by SOC and PT for each treatment group and total
- Number and percentage of patients experiencing TEAEs leading to death by SOC and PT for each treatment group and total

Tables: Serious treatment-emergent AEs

- Number and percentage of patients experiencing Serious TEAEs by SOC and PT for each treatment group and total
- Number and percentage of patients experiencing Serious TEAEs leading to withdrawal of IMP by SOC and PT for each treatment group and total

- Number and percentage of patients experiencing Serious TEAEs related to IMP by SOC and PT for each treatment group and total

All AEs will be listed by patient including subject-id, treatment group, AE Term, SOC, PT, Time of onset (in relation to first dose of IMP), time of resolution (in relation to first dose of IMP), Intensity, Causality, Action taken, Outcome and a flag for TEAE/non-TEAE. The following listings will be provided:

- All AEs (including SAEs)
- All SAEs
- All AEs leading to withdrawal of IMP
- All AEs leading to hospitalization
- All AEs leading to death

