1. INTRODUCTION

The pivotal Phase 3 POLAR program, studying calmagafodipir for the prevention of chemotherapy induced peripheral neuropathy, consists of two studies: POLAR-A and POLAR-M.

- POLAR-A is a placebo controlled, randomised (1:1) Phase III study of calmagafodipir 5 µmol/kg in combination with mFOLFOX6 compared to placebo+mFOLFOX6 in patients with adjuvant treatment of stage III or high-risk stage II colorectal cancer.
- POLAR-M is a placebo controlled, randomised (1:1:1) Phase III study of calmagafodipir in two different doses, 2 µmol/kg and 5 µmol/kg in combination with mFOLFOX6 compared to placebo+mFOLFOX6 in patients with metastatic CRC.

Patient recruitment in the POLAR-A and POLAR-M studies was initiated in late 2018 with the first patient randomised in on January 15, 2019, in POLAR-A and on POLAR-M on January 21, 2019.

On January 23, 2020, the Sponsor announced that the US Food and Drug Administration (FDA) had issued a clinical hold in the US of the POLAR program. The implication was that recruitment and dosing of patients in the POLAR-M study was halted in the US. Based on the evaluation of the independent Drug Safety Monitoring Board (DSMB), the Sponsor's position was that the overall safety profile for PledOx supported the continuation of the POLAR program and both studies continued as planned in Europe and Asia with dosing and further recruitment.

On March 1, 2020, the Sponsor decided to place recruitment and dosing of patients in the POLAR program on hold. The decision followed interactions with the French regulatory authority, ANSM, and the clinical hold issued by the US Food and Drug Administration (FDA) earlier in the year and was due to 4 observed events related to seizure. The Sponsor maintained its position that these events are not related to calmagafodipir, a position which was also supported by the DSMB and an additional independent external evaluation of these cases.

On April 6, 2020, the Sponsor decided to close the POLAR program early with a data cut-off targeted for the third quarter 2020 (further detailed later in this document). The decision was taken after a recommendation from the DSMB to stop the studies due to an accumulation of severe allergic reactions, primarily observed after repeated dosing.

Based on the development of the POLAR studies, a re-assessment of the sample size assumptions is needed to determine a reasonable statistical approach to the analysis of the POLAR studies.

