6.1.1 Adverse Events of Special Interest

AEs/SAEs of special interest are selected based on following SMQs from the Medical Dictionary for Regulatory Activities (MedDRA):

- Convulsions
- Neuropathy
- Hypersensitivity

Data presentations

- Table: Number and percentage of patients with Convulsions, Neuropathy or Hypersensitivity related AEs by SOC and PT for each treatment group and total
- Table: Number and percentage of patients with Convulsions, Neuropathy or Hypersensitivity related SAEs by SOC and PT for each treatment group and total

Chemotherapy-related AEs/SAEs recorded in the eCRF are also of special interest. Examples of such events are peripheral sensory neuropathy, hematological toxicities, ANC, febrile neutropenia, WBC count and thrombocytopenia.

Data presentations

- Table: Number and percentage of patients with chemotherapy-related AEs by SOC and PT for each treatment group and total
- Table: Number and percentage of patients with chemotherapy-related SAEs by SOC and PT for each treatment group and total

IMP toxicity-related AEs/SAEs are recorded in the eCRF defined as an AE that is considered to be chemotherapy-related toxicity and also is possibly, probably or definitely related to the IMP treatment using the National Cancer Institute Common Terminology Criteria for Adverse Events (NCI-CTCAE) v4.03.

In SAS IMP toxicity will be derived as:

```
imp_tox=0;  
IF aechemtx EQ 'Yes' AND aere1 IN('Definitely Related',  
                                'Possibly Related',  
                                'Probably Related') THEN imp_tox=1;
```

where,

- aechemtx = Is this AE considered to be chemotherapy-related toxicity?
- aere1 = Is there a reasonable possibility of a causal relationship between the IMP treatment and the AE?

A patient is counted only once in case of multiple events for a given patient.

Data presentations

- Table: Number and percentage of patients with IMP toxicity-related AEs by SOC and PT for each treatment group and total
- Table: Number and percentage of patients with IMP toxicity-related SAEs by SOC and PT for each treatment group and total

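### Adverse events collected under the extended post-hold window with onset more than 30 days after the last IMP dose are listed but not counted by arm, and Section 6.1.1 leaves unclear whether its tables include them

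*SAP*

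**What the plan says.** Section 6.1 sets the collection window first. The basic rule is "All AEs including SAEs will be collected up to 30 days after the last administration of IMP", with an alternative added after the dosing hold: "or as of March 2nd., 2020, up to 30 days after the EOT".

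It then describes the end of the treatment-emergent period in more than one way. The opening definition has no upper limit. The next sentence has treatment-emergent events "end at the EOT visit (i.e. 14 days after the last dose of IMP"). The one after adds: "AEs will also be considered treatment-emergent if they are ongoing at first IMP infusion or start ≤ 30 days after the last dose of IMP". The allocation to study periods uses 30 days after the last IMP dose as the end of Period 2 (TEAE) and closes with "Period 3: Time of last dose of IMP + 31 days and onwards (non-TEAE").

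The reporting rule is categorical: "Non-TEAEs will not be presented in summary tables, only in listings". The summary tables named in Section 6.1, including those for serious events and events leading to death, are all restricted to TEAEs.

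Section 6.1.1 words its tables differently. An example is "Number and percentage of patients with Convulsions, Neuropathy or Hypersensitivity related AEs by SOC and PT for each treatment group and total". The chemotherapy-related and IMP-toxicity tables follow the same pattern. None carries a treatment-emergent qualifier, and none is exempted from the Section 6.1 rule.

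**The concern.** Collection was lengthened from the day after the 1 March 2020 hold, but the tabulation window was not lengthened with it. Data that the program chose to gather would be visible only patient by patient, with no count or percentage by treatment group.

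The events at stake matter to the safety account. The Introduction attributes the hold to seizure-related events and the closure to "an accumulation of severe allergic reactions, primarily observed after repeated dosing". Convulsions, hypersensitivity and neuropathy are the three special-interest groups, and chemotherapy-related events are also named as of special interest. A window tied to the last IMP dose, and not to chemotherapy, can miss events that arise if chemotherapy goes on without IMP. A fatal or serious event with onset after day 30 would likewise have no place in the AE tables.

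**Working it through.** The plan states no figure for this gap, so the check is a comparison of rules plus day arithmetic.

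**Inputs (Section 6.1)**
- Collection, earlier rule: last IMP dose + 30 days.
- Collection from 2 March 2020: EOT + 30 days.
- EOT: 14 days after the last IMP dose.
- TEAE period by the period allocation: to last IMP dose + 30 days.
- Period 3: day 31 onwards, non-TEAE, listings only.

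**Gap = end of collection − end of TEAE period, in days after the last IMP dose**

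| Situation | Collection ends | TEAE period ends | Collected but not tabulated |
|---|---|---|---|
| Collection closed under the earlier rule | day 30 | day 30 | 0 days |
| Extended rule, EOT at day 14 (SAP definition) | 14 + 30 = day 44 | day 30 | 14 days (days 31–44) |
| Extended rule, EOT at day 42 (assumed) | 42 + 30 = day 72 | day 30 | 42 days |
| Extended rule, EOT at day 98 (assumed) | 98 + 30 = day 128 | day 30 | 98 days |

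Under the extended rule the gap equals the number of days from the last IMP dose to EOT, because both windows add 30 days. The last two rows assume a later EOT than the SAP states, for instance because chemotherapy continued without IMP.

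**How many patients?** The SAP does not say how many were followed under each rule. Table 1 of the Introduction gives 582 patients dosed and 205 with at least 12 IMP cycles, so 582 − 205 = 377 had fewer than 12 (377/582 = 64.8%; POLAR-A 297 − 107 = 190, POLAR-M 285 − 98 = 187). This is only a loose upper bound on those whose IMP could have been cut short of 12 cycles by the hold. It also includes pre-hold stoppers and any shorter courses, since POLAR-A chemotherapy is for up to 6 months and POLAR-M for at least 3.

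**Do the Section 6.1.1 tables escape the rule?**
- For inclusion of Period 3: these tables say AEs or SAEs, whereas every table in Section 6.1 says TEAEs.
- Against: Section 6.1.1 sits under Section 6.1, whose bar covers summary tables without exception, and 6.1.1 states no exemption.

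The second reading is the stronger, but a programmer could defend either.

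**The case against.** A 30-day post-dose limit for TEAEs is an ordinary choice, and nothing is hidden. All AEs, SAEs and AEs leading to death are listed with treatment group, onset relative to first dose and a TEAE flag. Events collected after the hold with onset within 30 days of the last dose are still tabulated. Neuropathy is summarised by arm through FACT/GOG at each visit, with data to 12 months (Sections 2.5, 5.1.1, 5.3.7), and haematology by arm through the assessment visits (Section 6.2). Deaths enter the survival analyses in Sections 6.10 to 6.12. All of this stands. It limits the consequence, but a listing still gives no by-arm count of late AEs, SAEs or fatal AEs.

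Three stronger readings are tempting, and the SAP does not support them:

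- *That special-interest events after day 30 can never reach a by-arm table.* The wording of Section 6.1.1 leaves this open.
- *That the rule flatters PledOx, because patients who stop IMP for an allergic reaction have their window closed early.* This needs such stops to be more frequent on PledOx and the patients to be still on chemotherapy in March 2020. The SAP gives neither fact. Where collection ended under the earlier rule there are no later events to tabulate, so that part concerns collection and not tabulation. From 1 March 2020 dosing was put on hold across the program, so many later stops follow a calendar date and not the arm.
- *That about 65% of patients, or most of the remaining oxaliplatin period, fall outside the tables.* The 377 are not a count of affected patients. The long gaps need an EOT later than the 14 days that Section 6.1 gives. The extension makes a later EOT plausible, but the visit structure is left to the protocol (Section 2.3).

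**Conclusion.** The defect is real and modest. Followed as written, Section 6.1 collects AEs, SAEs and fatal AEs that it then excludes from every summary table it names. The gap is 14 days per patient under the extended rule on the SAP's own EOT definition, longer only if EOT falls later, and zero for patients closed under the earlier rule. For the Section 6.1.1 tables the finding is an ambiguity that has to be settled, not a proven exclusion. Neither the number of patients concerned nor any difference between arms can be derived from the SAP. The conclusion rests on taking the period allocation as the operative TEAE definition; the competing end points in the same section are themselves part of what needs repair.

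**What to change.** - Keep the TEAE tables as they are.
- Exempt Period 3 from the listings-only rule in Section 6.1. Add separate by-treatment tables of Period 3 AEs, SAEs, AEs leading to death, the three special-interest groups and chemotherapy-related AEs.
- Use the safety set by treatment actually received, as Section 3.1 defines it, and not by randomised arm.
- Do not pool all dosed patients to the end of collection, because that mixes two ascertainment limits. Restrict the denominators to patients followed under the extended rule, or show the number under each rule by treatment, and footnote both limits.
- State in Section 6.1.1 whether its tables are restricted to TEAEs.
- Give one TEAE end point in Section 6.1 in place of the three now there (open-ended, EOT at 14 days, 30 days).

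The cost is a wording change and a few extra tables from data already collected. The new tables are descriptive only. They cannot recover late events in patients whose collection closed under the earlier rule.

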6.1.1 Adverse Events of Special Interest

AEs/SAEs of special interest are selected based on following SMQs from the Medical Dictionary for Regulatory Activities (MedDRA):

- Convulsions
- Neuropathy
- Hypersensitivity

Data presentations

- Table: Number and percentage of patients with Convulsions, Neuropathy or Hypersensitivity related AEs by SOC and PT for each treatment group and total
- Table: Number and percentage of patients with Convulsions, Neuropathy or Hypersensitivity related SAEs by SOC and PT for each treatment group and total

Chemotherapy-related AEs/SAEs recorded in the eCRF are also of special interest. Examples of such events are peripheral sensory neuropathy, hematological toxicities, ANC, febrile neutropenia, WBC count and thrombocytopenia.

Data presentations

- Table: Number and percentage of patients with chemotherapy-related AEs by SOC and PT for each treatment group and total
- Table: Number and percentage of patients with chemotherapy-related SAEs by SOC and PT for each treatment group and total

IMP toxicity-related AEs/SAEs are recorded in the eCRF defined as an AE that is considered to be chemotherapy-related toxicity and also is possibly, probably or definitely related to the IMP treatment using the National Cancer Institute Common Terminology Criteria for Adverse Events (NCI-CTCAE) v4.03.

In SAS IMP toxicity will be derived as:

```
imp_tox=0;  
IF aechemtx EQ 'Yes' AND aere1 IN('Definitely Related',  
                                'Possibly Related',  
                                'Probably Related') THEN imp_tox=1;
```

where,

- aechemtx = Is this AE considered to be chemotherapy-related toxicity?
- aere1 = Is there a reasonable possibility of a causal relationship between the IMP treatment and the AE?

A patient is counted only once in case of multiple events for a given patient.

Data presentations

- Table: Number and percentage of patients with IMP toxicity-related AEs by SOC and PT for each treatment group and total
- Table: Number and percentage of patients with IMP toxicity-related SAEs by SOC and PT for each treatment group and total

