The POLAR studies were designed based on the following sample size assumptions:

- POLAR-A: With 112 patients per group, the POLAR-A study has 91% power to detect a reduction (improvement) from 40% to 20% (OR = 0.375) in the primary endpoint using two-sided test controlled at the 0.05 type-I error rate. To account for 20% dropout in the study, in total 280 patients (140 patients per arm) will be randomised.
- POLAR-M: With 112 patients per group, the POLAR-M study has 91% power to detect a reduction (improvement) from 40% to 20% (odds ratio = 0.375) in the primary endpoint using two-sided test controlled at the 0.05 type-I error rate. To account for 20% dropout in the study, in total 420 patients (140 patients per arm) will be randomised.

Table 1: Patient disposition in the POLAR studies

	POLAR-A	POLAR-M	Total
Number of patients randomised	301	290	591
Number of patients dosed with ≥ 1 cycle of IMP	297	285	582
Number of patients dosed with ≥ 6 cycles of IMP	257	194	451
Number of patients dosed with ≥ 12 cycles of IMP	107	98	205

A total of 591 patients was randomised in the POLAR program and 582 patients dosed, of which 451 patients completed 6 cycles and 205 patients completed 12 cycles (see Table 1).

There are two main contributing factors to take into account when designing a reasonable statistical approach to the analysis of the POLAR studies:

- 1) POLAR-M only randomised 290 out of the planned 420 patients. This, together with the reduced dosing of patients (see bullet 2 below) means a separate primary analysis based on this data set cannot be supported.
- 2) Due to the Sponsor's decision to place the dosing of patients on hold on March 1, 2020, not all patients have had sufficient dosing of IMP to expect the full treatment effect of active treatment as assumed in the sample size calculation.

Taking these two aspects into consideration account (the fewer number of randomised patients and the reduced dosing of patients) a reasonable statistical approach is to conduct a combined primary analysis across the two studies, with the data from the two studies regarded as strata, based on a modified ITT analysis set defined by the eligibility of dosing with IMP as intended in the clinical study protocol. In addition, a standalone analysis of the primary endpoint in the fully recruited POLAR-A study will be conducted if the combined analysis is statistically significant. This approach will be further detailed in this document.

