3.1 Analysis Sets

The analysis set “All randomised patients (ITT)” consists of all patients who were assigned a randomisation number, irrespective of the treatment they received, if any.

The modified ITT (mITT) analysis set includes patients that fulfil at least one of the following criteria:

1. the patient was randomised prior to December 1, 2019 (ie the patient was eligible for at least 3 months of IMP) and had at least one post-baseline assessment for efficacy, or
2. the 3 month Assessment Visit occurred prior to 1 March, 2020, or
3. the patient received the 6th cycle of IMP after 1 March, 2020.

Patients will be analysed according to the treatment they are assigned to at randomisation, irrespective of what treatment they actually received.

The safety analysis set (SAF) consists of all randomised patients who receive at least one dose of IMP. Patients will be analysed according to the randomised study treatment actually received.

The list of patients to be included in each of the analysis sets is to be agreed between the project statistician and the Sponsor prior to unblinding, once all study data is available.

All enrolled patients will be listed indicating their membership to each analysis set along with the reason for exclusion.

The PK population (POLAR-M only) includes a subset of patients at pre-selected sites in all participating regions, where blood samples will be collected for pharmacokinetics and ECG assessments.

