4. STUDY PATIENTS

Study Patients data will be presented by descriptive statistics by treatment group and total. Continuous variables will be summarised by number of patients (n), mean, standard deviation (SD), minimum, median and maximum, while categorical variables by counts and percentages. Unless otherwise stated the calculation of proportions will be based on the size of the analysis set of interest.

Listings will include all enrolled patients unless specified otherwise.

Summaries for Study Patients variables will be provided for both the mITT and the safety analysis set.

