6. SAFETY EVALUATION

All safety evaluations will be performed on the safety analysis set unless specified otherwise.

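### The special-interest adverse event tables give only crude SOC/PT percentages of all dosed patients, with no patient count per SMQ and nothing by IMP cycle, although the programme closed for reactions seen mainly after repeated dosing

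*SAP*

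**What the plan says.** Section 6.1.1 selects events of special interest by three MedDRA SMQs (Convulsions, Neuropathy, Hypersensitivity). The planned output is "Table: Number and percentage of patients with Convulsions, Neuropathy or Hypersensitivity related AEs by SOC and PT for each treatment group and total", with a matching table for SAEs. Under Section 6.1 a patient counts once in each SOC and once in each PT. That section leaves intensity to the listings, and time of onset is likewise specified only for the listings.

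The denominator follows from three places. Section 6: "All safety evaluations will be performed on the safety analysis set unless specified otherwise". Section 3.1: the safety set "consists of all randomised patients who receive at least one dose of IMP". Section 4: "Unless otherwise stated the calculation of proportions will be based on the size of the analysis set of interest". This last rule is written for the patient-characteristics section, but nothing in Section 6 replaces it.

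The Introduction describes the background. The hold on dosing followed four seizure-related events. The DSMB then recommended stopping "due to an accumulation of severe allergic reactions, primarily observed after repeated dosing". On exposure it reports "582 patients dosed, of which 451 patients completed 6 cycles and 205 patients completed 12 cycles". Section 4.4.1 already plans a table of patients receiving IMP at each cycle, by treatment group.

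**The concern.** The safety question that ended the programme concerns a group of reactions and how they depend on the number of doses. The planned tables show neither directly.

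- **Group.** An SMQ can draw its terms from several SOCs. Split by SOC and PT, it becomes a set of small rows. A patient with two PTs appears in both, so the rows cannot be added to give patients with any hypersensitivity event. The wording also places the three SMQs in one phrase, so an overall total in such a table could mix hypersensitivity with neuropathy, the condition the drug is meant to prevent.
- **Repeated dosing.** No adverse event table is by cycle or adjusted for exposure. Patients whose dosing ended early stay in the denominator with the same weight as those who received all 12 cycles.

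At stake is whether the clinical study report can state, from its tables, how many patients per arm had a hypersensitivity or convulsion event and how the risk developed over the course.

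**Working it through.** **1. Exposure figures (SAP Table 1).** The totals reproduce: 297 + 285 = 582 dosed; 257 + 194 = 451 with at least 6 cycles; 107 + 98 = 205 with at least 12.

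- Reached 6 cycles: 451/582 = 77.5% (POLAR-A 257/297 = 86.5%; POLAR-M 194/285 = 68.1%).
- Reached 12 cycles: 205/582 = 35.2% (POLAR-A 107/297 = 36.0%; POLAR-M 98/285 = 34.4%).

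**2. Effect of the denominator alone.** If every event occurred in patients who reached a given cycle, dividing by all dosed patients instead of by those patients shrinks the percentage by 582/451 = 1.29 at 6 cycles and 582/205 = 2.84 at 12 cycles.

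**3. Illustration of crude against full-course risk.** The SAP gives no event counts or onset cycles, so the following are assumptions:

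- a constant first-event risk *h* of 0.5%, 1% or 2% per cycle, from onset cycle *s* = 2, 4 or 7, and zero before;
- patients dosed at cycle *c*, N(c), interpolated linearly between cycles 1, 6 and 12.

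Crude percentage = Σ N(c) × (1 − h)^(c − s) × h / N(1), summed over c = s to 12. Full-course risk = 1 − (1 − h)^(13 − s).

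Worked case, combined data, s = 7, h = 1%: N(7) to N(12) = 410, 369, 328, 287, 246, 205. Expected first events = 0.01 × (410 + 369 × 0.99 + … + 205 × 0.99^5) = 18.07. Crude = 18.07/582 = 3.10%. Full course = 1 − 0.99^6 = 5.85%. Ratio 1.89.

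Results for h from 0.5% to 2%:

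| Onset cycle | Crude, combined | Full course | Ratio, combined | Ratio, POLAR-A | Ratio, POLAR-M |
|---|---|---|---|---|---|
| 2 | 3.67–13.82% | 5.36–19.93% | 1.44–1.46 | 1.35–1.37 | 1.55–1.58 |
| 4 | 2.77–10.55% | 4.41–16.63% | 1.58–1.59 | 1.45–1.47 | 1.73–1.75 |
| 7 | 1.57–6.08% | 2.96–11.42% | 1.88–1.89 | 1.74–1.75 | 2.05–2.06 |

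The ratio hardly depends on *h*. It depends on when risk begins and on which study is used, and runs from 1.35 to 2.06.

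**4. Limits of the illustration.** Table 1 pools all arms, including placebo and 2 µmol/kg. The counts at later cycles may already exclude patients who stopped after a reaction, a small effect at these risks.

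**The case against.** - **A crude percentage over the safety set is conventional and valid.** This stands. It estimates the proportion of dosed patients with an event, and the SAP does not present it as full-course risk. Nor was 12 cycles every patient's planned course: POLAR-A is described as up to 6 months of chemotherapy and POLAR-M as at least 3 months.
- **The table shells are in a separate document, and the listings hold arm, PT and onset for each patient.** This stands in part. The shells might contain a row per SMQ, and the counts could be built from the listings. The SAP text does not require either.
- **A reader might infer that the comparison between arms is biased.** The documents do not show this. The sponsor's March 2020 hold on dosing applied across the programme. Bias could arise if reactions ended dosing more often on active drug, but the SAP gives no data on that.
- **A reader might infer that the IMP toxicity flag hides allergic reactions.** Its code, beginning "IF aechemtx EQ 'Yes' AND aere1 IN('Definitely Related", requires attribution to both chemotherapy and IMP, so an event attributed to IMP alone is not flagged. But the code matches the definition stated beside it, and the Hypersensitivity tables use neither the flag nor causality. Events attributed to IMP alone still enter the tables of IMP-related TEAEs and serious TEAEs in Section 6.1. The flag therefore lowers neither the hypersensitivity counts nor the IMP-related counts. What remains is a misleading table title.

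**Conclusion.** The point holds as a gap in the planned safety summaries. Section 6.1.1 provides no patient count per SMQ and nothing by cycle, although the SAP itself ties the decisive signal to repeated dosing and reports that 35% of dosed patients reached 12 cycles. If risk continues at later cycles, the crude percentage understates the risk of a full course. The direction follows from Table 1; the size does not. The range of about 1.35 to 2.1 rests on assumed per-cycle risks, assumed onset cycles, linear interpolation and exposure counts pooled over arms. It should not be read as an estimate for this drug. The point does not show that the crude figures are wrong as proportions of dosed patients.

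**What to change.** In Section 6.1.1:

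1. Add, by arm, one row per SMQ with the number and percentage of patients with at least one event, for AEs and for SAEs.
2. For Hypersensitivity and Convulsions, add first events by IMP cycle of onset. The denominator is patients dosed at that cycle and still free of the event. The Section 4.4.1 counts are the starting point, but patients with an earlier event must be removed.
3. For the same two SMQs, add cumulative incidence by cycle and arm, censored at last IMP dose + 30 days. This agrees with the treatment-emergent period in Section 6.1.
4. At most, retitle the IMP toxicity tables as AEs attributed to both chemotherapy and IMP. The definition can stay.

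The cost is SAP wording and a few tables from the AE and dosing data already collected. The downside is small numbers at late cycles, with wide intervals, so these tables should be read as descriptive.
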